Figure 2 Randomization Scheme for MuSK-Ab+ Population 11

Figure 3 Study Flow Diagram..... 12

LIST OF ABBREVIATIONS

Abbreviation	Definition
AChR-Ab+	Acetylcholine receptor antibody positive
ADA	Anti-drug antibody(ies)
AE	Adverse event
AESI	Adverse event of special interest
ALP	Alkaline phosphatase
ALT	Alanine aminotransferase
ANC	Absolute neutrophil count
anti-AChR	anti-acetylcholine receptor antibody
anti-MuSK	anti-muscle-specific kinase antibody
AST	Aspartate aminotransferase
CI	Confidence interval
CRF	Case report form
eCDF	Empirical cumulative distribution function
ECG	Electrocardiogram
eCRF	Electronic case report form
FAS	Full Analysis Set
Ig	Immunoglobulin
IP	Investigational product
IST	Immunosuppressive therapy(ies)
ITT	Intent-to-treat
IV	Intravenous(ly)
IVIg	Intravenous immunoglobulin
IXRS	Interactive voice/web response system
MG	Myasthenia gravis
MG-ADL	Myasthenia Gravis Activities of Daily Living
MGC	Myasthenia Gravis Composite
MGFA	Myasthenia Gravis Foundation of America
MGQOL-15r	Myasthenia Gravis Quality of Life-15, revised
MI	Multiple imputation
MMRM	Mixed-effects model for repeated measures
MuSK-Ab+	Muscle-specific kinase antibody positive
OLP	Open-label period
PAS	Per-protocol analysis set
PK	Pharmacokinetic(s)
PLEX	Plasma exchange

PRO	Patient-reported outcome
PT	Preferred term
QMG	Quantitative Myasthenia Gravis
QOL	Quality of life
RCP	Randomized controlled period
SAE	Serious adverse event
SAP	Statistical analysis plan
SC	Subcutaneous
SFP	Safety Follow up Period
SOC	System organ class
SPP	Statistical programming plan
TEAE	Treatment-emergent adverse event
TESAE	Treatment-emergent serious adverse event
ULN	Upper limit of normal

1. Introduction

This document describes the statistical analysis plan for protocol VIB0551.P3.S1(20230049), a Randomized, Double-blind, Multicenter, Placebo-controlled Phase 3 Study with Open-label Period to Evaluate the Efficacy and Safety of Inebilizumab in Adults with Myasthenia Gravis (MG).

2. Study Overview

2.1 Study Objectives and Endpoints

The objectives and corresponding endpoints are listed in Table 1 below:

Table 1 Study Objectives and Endpoints

Primary objective	Endpoints/variables

 To assess whether inebilizumab can reduce MG-related disability 	
 Change from baseline in Myasthenia Gravis Activities of Daily Living (MG-ADL) score at Week 26 in the overall study population, i.e., the Acetylcholine receptor antibody positive (AChR-Ab+) and Muscle-specific kinase antibody positive (MuSK-Ab+) populations.
Secondary objectives	Endpoints/variables

 To evaluate whether inebilizumab can reduce the frequency of MG exacerbations To evaluate whether inebilizumab can improve MG-related quality of life (QOL) To evaluate the effect of inebilizumab on corticosteroid usage 	
Key secondary endpoints:
 
 Change from baseline in Quantitative Myasthenia Gravis (QMG) score at Week 26 in the overall study population. Change from baseline in MG-ADL score at Week 26 in the AChR-Ab+ population. Change from baseline in QMG score at Week 26 in the AChR-Ab+ population. Change from baseline in MG-ADL score at Week 26 in the MuSK-Ab+ population. Change from baseline in QMG score at Week 26 in the MuSK-Ab+ population. 
Other secondary endpoints:
 
 Proportion of subjects with both (1) ≥ 3-point improvement in MG-ADL score at Week 26 and (2) no use of rescue therapy between Day 28 and Week 26 in the overall study population, AChR+ and MuSK-Ab+, and at Week 52 and no use of rescue therapy between Day 28 and Week 52 in AChR-Ab+ population. Change from baseline in MG-ADL score at Week 52 in the AChR-Ab+ population. Change from baseline in QMG score at Week 52 in the AChR-Ab+ population. Change from baseline in Myasthenia Gravis Composite (MGC) score at Week 26 in the overall study population, AChR-Ab+ and MuSK-Ab+ and at Week 52 in AChR-Ab+ population.

	
 • Change from baseline in Myasthenia Gravis Quality of Life-15, revised (MGQOL-15r) score at Week 26 in the overall study population, AChR-Ab+ and MuSK-Ab+ and at Week 52 in AChR-Ab+ population. • Patient Global Impression of Change (PGIC) score at Week 26 in the overall study population, AChR-Ab+ and MuSK-Ab+ and at Week 52 in AChR-Ab+ population. • Time to first exacerbation by Week 26 in the overall study population, AChR-Ab+ and MuSK-Ab+ and by Week 52 for AChR-Ab+ populations. • The proportion of subjects with steroid tapered to ≤ 5 mg/day steroid at Week 26 for the overall study population, AChR-Ab+ and MuSK-Ab+ and at Week 52 for AChR-Ab+ population. • The proportion of subjects in whom steroid dose was reduced by $\geq 50\%$ from baseline by Week 26 for the overall study population, AChR-Ab+ and MuSK-Ab+ and by Week 52 for AChR-Ab+ population. • Proportion of subjects achieving minimal symptom expression, defined as MG-ADL= 0 or 1, at Week 26.

 • To evaluate the safety and tolerability of inebilizumab in MG 	
 • The safety and tolerability of inebilizumab as measured by the incidence of treatment-emergent adverse events (TEAEs), adverse events of special interest (AESIs), and treatment-emergent serious adverse events (TESAEs). • Clinical Laboratory. • Vital signs. • Electrocardiogram (ECG).

 • To characterize the pharmacokinetic (PK) profile and immunogenicity of inebilizumab in subjects with MG 	
 • Serum concentration of inebilizumab. • Anti-drug antibody (ADA) status and titer.
Exploratory objectives	Endpoints/variables

Baseline is defined as the last non-missing valid observation prior to the 1st Investigational product (IP) administration during RCP. In cases where measurements are taken on the same day as the first administration of IP and no time is reported, it will be assumed that these measurements are taken prior to the first administration of IP.

2.2 Study Design Overview

This study is a phase 3, randomized, double-blind, placebo-controlled study, to be conducted at approximately 100 study sites. Approximately 230 subjects (188 AChR-Ab+ and 42 MuSK-Ab+) will be enrolled. The study includes 4 periods, a screening period, a randomized controlled period (RCP, 52 weeks for AChR-Ab+ population and 26 weeks for MuSK-Ab+ population), an optional open-label period (OLP, up to 3 years), and an optional safety follow up period (SFP, up to 2 years after the last IP dose administration).

Subjects who do not have anti-AChR or anti-MuSK antibodies are not eligible and will not be enrolled. Subjects with MGFA classification II, III, or IV disease, MG-ADL score between 6 and 10 with > 50% of this score attributed to non-ocular items or a MG-ADL score ≥ 11 , and QMG score ≥ 11 are eligible for this study. These criteria define a population of subjects with generalized MG and inadequate symptom control.

Within each population, subjects will be stratified by region first (non-Japan vs Japan). In the non-Japan population, subjects will be further stratified according to baseline disease severity ('Baseline QMG score = 11-15' vs 'Baseline QMG score ≥ 16 ') and baseline corticosteroid use ('prednisone > 5 mg/day' vs 'prednisone ≤ 5 mg/day'), and randomized 1:1 to receive either IV inebilizumab 300 mg or placebo ([Figure 1](#) and [Figure 2](#)). In the Japan population, no further stratification will be applied due to the small sample size expected, and subjects will be randomized 1:1 to receive either IV inebilizumab or placebo.

The duration of the RCP is 52 weeks for the AChR-Ab+ population ([Figure 1](#)) and 26 weeks for the MuSK-Ab+ population ([Figure 2](#)). The primary endpoint of the study is change from baseline in MG-ADL score at Week 26 in the overall study population (AChR-Ab+ and MuSK-Ab+ populations).

Subjects who enter the study on prednisone > 5 mg/day (or equivalent dose of another corticosteroid) will have their corticosteroid dose tapered per protocol, starting at Week 4 of the RCP. Steroid tapering will continue until the subject is on a dose of prednisone 5 mg/day; the dose of prednisone 5 mg/day will then be continued until the end of the RCP. Corticosteroid treatment will not be initiated if the subject is not being treated with those at the time of randomization.

The dose of azathioprine, mycophenolate mofetil, mycophenolic acid, and Acetylcholinesterase inhibitors must remain stable throughout the RCP. Tacrolimus is allowed in Japan only.

[figure not shown]
All subjects who complete the RCP will have the option to enroll in a 3-year OLP. In the OLP, further tapering of corticosteroids is at the discretion of the investigator. Tapering of non-steroidal immunosuppressive therapies (ISTs, e.g., azathioprine, mycophenolate mofetil, or mycophenolic acid) is recommended per standard of care.

Subjects who discontinued treatment during RCP or OLP will have the option to roll over into a 2-year safety follow up period (SFP).

- If a subject discontinues treatment during the RCP, this subject should be followed per the RCP schedules listed in the protocol. After the end of the RCP, subjects will be followed every 6 months until 2 years after the last dosing date.
- If a subject discontinues treatment during the OLP, this subject will be followed every 6 months until 2 years after the last dosing date.

[figure not shown]
The basic study flow diagram is presented in Figure 3.

Figure 1 Randomization Scheme for AChR-Ab+ Population

[figure not shown]
CS = corticosteroid; D = Day; IV = intravenous(ly); MG = Myasthenia Gravis; MG-ADL = Myasthenia Gravis Activity of Daily Living score; MGFA = Myasthenia Gravis Foundation of America; OLP = Open-Label Period; QMG = Quantitative Myasthenia Gravis scale; RCP = Randomized Controlled Period; SoC = Standard of Care.

Figure 2 Randomization Scheme for MuSK-Ab+ Population

CS = corticosteroid; D = Day; IV = intravenous(ly); MG = Myasthenia Gravis; MG-ADL = Myasthenia Gravis Activity of Daily Living score; MGFA = Myasthenia Gravis Foundation of America classification; MuSK-Ab+ = the population of subjects who are antibody positive for muscle-specific kinase; OLP = Open-Label Period; QMG = Quantitative Myasthenia Gravis scale; RCP = Randomized Controlled Period; SoC = standard of care.

Figure 3 Study Flow Diagram

~ = projected; AChR+ Ab = positive for antibodies against the acetylcholine receptor; IP = investigational product; MuSK+ Ab = positive for antibodies against muscle-specific kinase; n = number of subjects represent upper estimated limit and may be reduced based on enrollment of subjects in Japan; OLP = open label period; RCP = randomized controlled period.

- * Safety follow-up period for up to 2 years after the last IP dose will be offered to those subjects who have:
a) Discontinued IP during the RCP and completed all the RCP assessments, but have not entered the OLP.
b) Discontinued IP during the OLP and completed Early Discontinuation Visit in the OLP.

2.3 Sample Size

The primary endpoint is the change from baseline in MG-ADL score at Week 26 in the overall study population (i.e., the AChR-Ab+ and MuSK-Ab+ populations). Sample size was estimated using a 2-sided t-test. Approximately 230 subjects (188 subjects with AChR-Ab+ MG and 42 with MuSK-Ab+ MG) will be randomized at a 1:1 ratio to either receive inebilizumab or placebo. This sample size will provide more than 95% power to detect a true mean (population) treatment difference of 2 points in the MG-ADL score in the overall study population with a two-sided 0.05 alpha level assuming the common standard deviation is 4 using two-sided t-test.

The sample size of AChR-Ab+ subjects was also estimated using a 2-sided t-test, which will provide at least 90% power to detect a true mean (population) treatment difference of 2 points in change from baseline of MG-ADL with a 2-sided 0.05 alpha level. The sample size of MuSK-Ab+ population was estimated based on the feasibility of enrollment. Assuming the

common standard deviation is 4 and a two- sided 0.05 alpha level, the minimum detectable treatment difference in MuSK-Ab+ population is 2.5.

3. Statistical Methods

3.1 General Considerations

All efficacy analyses described below apply to the RCP unless stated otherwise. The efficacy endpoints will be summarized at scheduled visits during RCP and OLP in the overall study population, AChR+-Ab+ population, and MuSK+-Ab + population, respectively. For subjects in the OLP, the efficacy may also be summarized over the combined RCP and OLP to characterize the durability of the treatment effect, if applicable.

[figure not shown]
The safety endpoints will be summarized for the RCP, OLP and combined study periods, respectively in the overall study population, AChR+-Ab+ population, and MuSK+-Ab + population, respectively.

Tabular summaries will be presented by treatment group. Categorical data will be summarized by the number and percentage of subjects in each category. [REDACTED]

All hypothesis testing will be reported using 2-sided tests. Unless otherwise stated, nominal p-values will be reported. P-values will be rounded to 4 decimal places. The 95% confidence interval (CI) will be reported as appropriate.

The absolute change from baseline is computed as (visit value – baseline value). Percent change from baseline is computed as (visit value – baseline value) / baseline value x 100%. If either a visit value or the baseline value is missing, the absolute change from baseline and the percent change from baseline will also be set to missing.

All statistical calculations will be primarily performed using SAS® System Version 9.4 or higher.

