Corticosteroids can either be continued at a dose of prednisone 5 mg daily or can be tapered at the discretion of the Investigator. If a subject receives a dose of prednisone that is > 10 mg daily for > 8 consecutive weeks in the OLP, then the IP must be discontinued ([Section 6.3.1](#)). The rationale for this requirement is to reduce the potential risk of adverse effects associated with long-term combination of moderate- or high-dose corticosteroids and inebilizumab.

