  - k. Subjects who discontinue the IP during the OLP should complete an EDV and be asked to participate in the SFU Period (see [Section 6.1.4](#)).

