3.1.5 Missing data

Missing data will not be imputed except for the following:

QMG and MGC are allowed to have partially completed assessments per the system setup. If $\leq 50\%$ of the individual items in the questionnaire are missing at a visit, the missing items will be imputed using last observation carried forward (LOCF) before the calculation of the total scores. If $> 50\%$ of the individual items are missing, the total score at that visit will be considered as missing and no imputation will be applied. For the other questionnaires, the individual items in the questionnaire will be either all available or all missing per the system setup. No imputation will be applied to these missing records.

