3.4 Analyses Methods

3.4.1 Intercurrent events and Strategies

Potential intercurrent events such as discontinuing from the treatment, early discontinuing from the study, death, or initiating rescue therapy, which includes intravenous immunoglobulin (IVIg) or plasma exchange (PLEX), may occur during the study. Subjects who discontinue from the treatment and/or receive rescue therapy will be encouraged to stay in the study after those intercurrent events and data will be collected through planned study completion. These intercurrent events will be addressed using different strategies in the efficacy and safety analyses as appropriate. The following analyses strategies will be used and detailed components of each strategy are included in the sub-sections under Section 3.4 and Section 3.5.

Treatment-policy strategy: The analyses will include all data captured in each study period, defined as the period after randomization to the conclusion of the last scheduled visit in the corresponding study period regardless of the rescue therapy use.

While on-treatment strategy: The analyses will include all data captured while subjects are on treatment during the RCP, [REDACTED]

All efficacy analyses described below apply to the RCP unless stated otherwise. The efficacy endpoints will be analyzed in the overall study population, AChR-Ab+ population, and MuSK-Ab + population, respectively, [REDACTED] as suitable. Supplementary analyses using treatment-policy strategy will be conducted for primary endpoint and key secondary endpoints to assess the robustness of the conclusions. For subjects in the OLP, the efficacy may also be summarized based on OLP and the combined RCP and OLP using treatment-policy strategy, if applicable.

The safety endpoints will be summarized for the RCP, OLP, **and combined RCP and OLP** separately and analyzed using treatment-policy strategy. Summary of AEs/ SAEs/ AESIs, CD20+ B-cell count, and Serum Immunoglobulins would be provided for subjects based on combined RCP and OLP, and based on SFP if applicable.. [REDACTED] may be conducted using while on-treatment strategy for TEAE/TESAE/AESI as needed.

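### Open-label efficacy is labelled treatment policy, but after IP is stopped in the OLP the schedule collects MG scores once only, so the durability summaries are in effect on-drug and observed-case

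*SAP*

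**What the plan says.** **Purpose and status.** SAP 3.1 plans efficacy summaries at scheduled visits in both the RCP and the OLP. It adds, as an option, that "the efficacy may also be summarized over the combined RCP and OLP to characterize the durability of the treatment effect". SAP 3.1.2 bases the OLP efficacy summaries on the Open-label Analysis Set.

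**Label.** The strategy is named in SAP 3.4.1, not in 3.1: "the efficacy may also be summarized based on OLP and the combined RCP and OLP using treatment-policy strategy, if applicable". The same section says that subjects who stop treatment or receive rescue are encouraged to stay, and that their data are collected up to the planned end of the study. It makes no exception for the OLP.

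**What happens after IP is stopped in the OLP.** Protocol Table 5, footnote k: "Subjects who discontinue the IP during the OLP should complete an EDV and be asked to participate in the SFU Period". SAP 2.2 agrees: "If a subject discontinues treatment during the OLP, this subject will be followed every 6 months until 2 years after the last dosing date". In the RCP, by contrast, Protocol 6.3.1 asks stoppers to complete all remaining RCP visits and assessments other than those tied to dosing.

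**Reasons for stopping.** Protocol 6.1.3 requires that a subject on prednisone above 10 mg daily stops IP if this continues "for > 8 consecutive weeks in the OLP, then the IP must be discontinued". Protocol 6.3.1 also records lack of efficacy as a possible reason.

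**Missing scores.** SAP 3.1.5: "Missing data will not be imputed except for the following". The exceptions concern partly completed QMG and MGC questionnaires, not missed visits.

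**The concern.** A treatment-policy summary includes outcomes after treatment is stopped. If those outcomes are not collected or imputed, the table describes the people who remained on drug, whatever its label says.

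That matters for durability over up to three open-label years. If subjects who worsen are more likely to stop, the mean among those observed can hold steady or improve while the whole cohort does not. A reader told that the strategy is treatment policy would take the figures as covering everyone who entered the OLP.

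**Working it through.** **1. Trace of MG scores after stopping IP**

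| | RCP stopper | OLP stopper |
|---|---|---|
| At stopping | stays on RCP schedule | one EDV, sharing the Day 1093 column of Protocol Table 5, with MG-ADL, QMG and MGC |
| Afterwards | remaining RCP visits, with MG scores | safety follow-up, Protocol Table 6: AEs, concomitant medications, blood tests; no MG-ADL, QMG or MGC |

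Table 5 schedules MG-ADL at 11 OLP visits; Table 6 schedules it at none. Protocol 9.4 nevertheless mentions durability summaries for subjects in the SFU Period.

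Example: more than 8 weeks (56 days) from OLP Day 1 puts the earliest steroid-rule stop at about Day 58. With the bisected windows of SAP 3.1.4, the boundary between Days 15 and 92 is (15 + 92)/2 = 53.5, so this EDV fills the Day 92 window. The next 8 scheduled scores (Days 183, 275, 365, 456, 547, 729, 911 and 1093) are empty.

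**2. Size of the effect on a mean**

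The plan states no figure to reproduce, and the documents give neither an OLP stopping rate nor post-stop scores. The inputs below are assumptions. Let f be the share stopped and d the stoppers' mean score minus the stayers' (higher is worse). Then

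full-cohort mean − observed mean = [(1 − f)·S + f·(S + d)] − S = f·d,

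where S is the stayers' mean. A positive value means that the observed figure looks better than the cohort.

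| f | d = −1 | d = 0 | d = 1 | d = 2 | d = 4 |
|---|---|---|---|---|---|
| 5% | −0.05 | 0 | 0.05 | 0.10 | 0.20 |
| 10% | −0.10 | 0 | 0.10 | 0.20 | 0.40 |
| 20% | −0.20 | 0 | 0.20 | 0.40 | 0.80 |
| 30% | −0.30 | 0 | 0.30 | 0.60 | 1.20 |

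For scale, Protocol 6.2.5.4 gives a minimal important difference of 2 MG-ADL points.

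**3. Does added steroid change the direction?**

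A simulation of the nine OLP visits from Day 92 to Day 1093 assumed no average drift, individual slopes with SD 1.2 points per year, visit-to-visit SD 1.5, 1% unrelated stops per visit, and a stop once worsening from OLP entry exceeds 5, 4 or 3 points. After such a stop, added steroid lowers the score by 0, 2, 4 or 6 points. The entries are full-cohort minus observed mean change at Day 1093.

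| Stop if worse by more than | Unobserved | Benefit 0 | 2 | 4 | 6 |
|---|---|---|---|---|---|
| 5 | 16% | 0.60 | 0.45 | 0.28 | 0.11 |
| 4 | 25% | 1.04 | 0.73 | 0.40 | 0.07 |
| 3 | 39% | 1.67 | 1.09 | 0.48 | −0.14 |

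Eleven of the 12 assumed cases overstate and one reverses.

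**4. Effect on a proportion**

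Take 100 entrants, 70 of whom would be responders, and let 20 stop.

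- All 20 are non-responders (an extreme case): observed-case rate 70/80 = 87.5%, against 70/100 = 70% over all entrants.
- Stopping is unrelated to response, so 14 of the 20 are responders: observed-case rate 56/80 = 70%, with no distortion. Counting stoppers as non-responders gives 56/100 = 56%.

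The second case shows the cost of the non-responder rule: it is conservative when stopping has nothing to do with MG.

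**The case against.** Several points on the other side stand.

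- **Stoppers do not go wholly unscored.** A reader might infer that they have no further MG scores. The EDV supplies one set, which enters the visit window where it falls. Only scores after the EDV are absent.
- **The direction is not guaranteed.** A reader might infer that durability is overstated by construction. The documents do not support that. The steroid rule applies whatever the reason for the steroid, and its stated rationale is safety. Added steroid may improve scores. Stops for adverse events, laboratory criteria, pregnancy or choice need not track MG worsening. Subjects rescued with IVIg or PLEX may continue (Protocol 7.2.2), so many who worsen remain in the summaries.
- **The stakes are limited.** The combined and strategy-labelled summaries are optional. All OLP summaries are outside the testing hierarchy.
- **Redaction.** Parts of SAP 3.4.1 and the by-period baseline definitions are blacked out and could hold further OLP rules.

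The strongest defence is that the label fits the SAP's own definition: "The analyses will include all data captured in each study period, defined as the period after randomization to the conclusion of the last scheduled visit", regardless of rescue. Post-rescue OLP data are indeed scheduled. But the same section also relies on data continuing after treatment discontinuation, and the OLP schedule does not provide that. Nor does the optional wording cover everything, since SAP 3.1 and 3.1.2 commit to OLP efficacy summaries.

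On direction, Protocol 7.2.1 allows steroid for non-MG conditions only short term and with medical monitor approval, and the RCP taper ends at 5 mg daily. Sustained use above 10 mg daily is therefore more plausibly linked to MG than not. That supports likely overstatement, not certainty.

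**Conclusion.** The mismatch holds on the visible text: SAP 3.4.1 claims a strategy and a data flow that the protocol delivers in the RCP but not in the OLP. Beyond the EDV, the OLP and combined efficacy summaries are observed-case and in effect on-drug.

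Overstated durability is the likely direction. Its size is unknown: 0.2-1.2 MG-ADL points if 10-30% stop with a 2-4 point gap, and zero or reversed if stoppers would score the same or better. Confidence is high on the label and data flow and moderate on direction. The primary and key secondary Week 26 analyses are unaffected. No view is taken on the steroid rule itself.

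**What to change.** 1. In SAP 3.1 and 3.4.1, label the OLP and combined RCP and OLP efficacy summaries as while on treatment (observed case). The visible while-on-treatment definition covers the RCP only, so extend it to the OLP.
2. Reconcile two statements with the OLP and safety follow-up schedules: the SAP 3.4.1 statement about data collection to the planned end of the study, and the mention in Protocol 9.4 of efficacy in the SFU Period.
3. Beside the relabelled summaries, report at each OLP visit the proportion of all OLP entrants due at that visit who keep an improvement of at least 3 MG-ADL points from RCP baseline. Count subjects who have stopped IP or left the OLP as non-responders. This extends the rule in SAP 3.4.5.2, which already treats study discontinuation as non-response. A subject who has completed the planned doses through Day 911 has not stopped IP.
4. At each visit show numbers entered, observed, still on IP, and stopped by reason, with the steroid rule as its own category.

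No imputation of means is proposed; any single carry-forward rule for stoppers would be open to dispute.

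The cost is SAP wording, a clarification in Protocol 9.4, and a few tables from data already collected. The durability figures will look less favourable, and the responder proportion may be conservative where stops are unrelated to MG.
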